## **COMMUNICATION OF ISSUES**

In the event of any prohibition or restriction imposed (e.g., clinical hold) by an applicable Competent Authority in any area of the world, or if the investigator is aware of any new information which might influence the evaluation of the benefits and risks of a Pfizer product, Pfizer should be informed immediately.

In addition, the investigator will inform Pfizer immediately of any urgent safety measures taken by the investigator to protect the study patients against any immediate hazard, and of any serious breaches of this NI study protocol that the investigator becomes aware of.

Redacted

### **13. LIST OF TABLES**

Not applicable.

### **14. LIST OF FIGURES**

Not applicable.

Redacted

**ANNEX 1. LIST OF STAND-ALONE DOCUMENTS**

None

**ANNEX 2. CASE REPORT FORM**

**ANNEX 3. COORDINATING INVESTIGATOR AGREEMENT**

**ANNEX 4. IRB/IEC APPROVAL**

**ANNEX 5. PATIENT'S INFORMATION SHEET AND INFORMED CONSENT**

**ANNEX 6. ECONOMIC REPORT**

Redacted

1 AMENDMENTS TO PREVIOUS VERSIONS

Not applicable: this is version 1.

2 INTRODUCTION

The purpose of this Statistical Analysis Plan (SAP) is to give a detailed description of the statistical analyses that will be carried out to generate the final report of the IMPACE study. This includes, on the one hand, a brief summary of the main characteristics of the study and, on the other, the objective of the SAP, which corresponds to the planning of the statistical analysis of the study.

Patients with chronic obstructive pulmonary disease (COPD) have been demonstrated to have an increased risk of pneumococcal disease.^{1,2} Pneumonia is frequent among patients hospitalized for COPD exacerbations and is associated with increased health care utilization and higher mortality. Nonpneumonic COPD exacerbations predict increased risk of subsequent exacerbations.³ Among community-acquired pneumonia (CAP) patients with the highest severity of disease who require hospitalization, COPD is the most common comorbidity. These two diagnoses, CAP and acute exacerbations of COPD (AECOPD), come together when a COPD patient has an exacerbation caused by CAP.⁴ Exacerbations are a significant component of the clinical course in COPD. Furthermore, as the disease progresses, exacerbations become more frequent.⁵

COPD exacerbations are defined as a complex of two or more respiratory symptoms (worsening dyspnea, cough, sputum production, chest tightness, or wheezing) related to the underlying COPD, with duration of 3 days or more, that require a change in treatment.⁶ AECOPD have a great impact on health status,⁷ disease progression,³ and prognosis.⁸ Up to 50%–70% of AECOPD can be attributed to respiratory infections by viruses or bacteria, even more in the most severe patients.⁹ They are often associated with the colonization of airways by multiple bacteria or viruses of low virulence that in normal conditions are part of the normal flora of the upper airway.¹⁰

Some studies have identified factors independently associated with bacterial growth, such as smoking and *H. influenzae*; longer periods between exacerbations and *S. pneumoniae*; or decrease in FEV1 and *P. aeruginosa*.¹¹ Traditionally, bacterial identification has been defined depending on the severity of the COPD, since *S. pneumoniae* and *M. catharralis* are isolated in patients with predicted FEV1 >50%, and *H. influenzae*, Enterobacteriaceae and *P. Aeruginosa* in those with predicted FEV1 <50%.^{11,12}

Therefore, considering *S. pneumoniae* appears to be more frequent in patients with mild/moderate COPD, these subjects might benefit from a preventive approach targeting this pathogen.

In terms of costs, COPD represents a significant burden on the healthcare system. Different studies relate the costs to the severity of the disease.¹³ The clinical course of COPD with multiple exacerbations has generated many economic studies analyzing these episodes. Anderson et al. in 2002 concluded that severe exacerbations represent 10 times the cost of a moderate exacerbation and around 60 times the cost of a mild-moderate episode. Similarly, exacerbations in severe COPD are 45 times more costly than in mild stages of the disease. The largest proportion of the cost of exacerbations is associated with hospitalizations, representing 65-85% of the total expense per acute episode.¹⁴

All this evidence supports the current recommendations for immunization of patients with COPD with vaccines against influenza and *Streptococcus pneumoniae*, aimed to help prevent infectious exacerbations.^{15,16} Existing studies suggest an additive effect in the prevention of all-cause mortality with influenza and pneumococcal vaccines given together in elderly people, including in those with chronic diseases. Although no significant reduction in mortality rate was seen with the pneumococcal vaccine (PPV23) alone, there was a decrease in mortality rate of 27.0% (20.0–34.0) in subjects who received both vaccines compared to 16.0% (6.0–24.0) in those who received the influenza vaccine alone.¹⁷ However, despite the existing recommendation, these vaccines are generally under-used, probably due to some persistent uncertainty about the benefits of vaccination.¹⁸

There are two types of pneumococcal vaccines, a 23-valent polysaccharide vaccine and a 13-valent conjugate vaccine. The 23-valent pneumococcal polysaccharide vaccine (PPV23) is approved and recommended for use in persons ≥ 2 years of age for the prevention of pneumonia and pneumococcal disease.¹⁹ In the past decades many studies have evaluated the effect of PPV23 in adults, and effectiveness in preventing invasive pneumococcal disease (IPD) has been reported, but with a short duration of protection and limited impact on the total burden of disease, even in countries with high uptake.^{20,21} Regarding the prevention of noninvasive pneumococcal pneumonia, the most common clinical presentation of the disease in adults, studies assessing the effectiveness of PPV23 show inconsistent results.²² The available studies focused specifically on COPD patients, do not show a clear effect on any of the outcomes evaluated (developing pneumonia or acute exacerbations).²³

The 13-valent pneumococcal conjugate vaccine (PCV13) was approved by the EMA for the prevention of IPD in adults ≥ 50 in 2011, and subsequently in 2013 for adults ≥ 18 years of age, based on immunogenicity studies.²⁴ Following the publication of the results of the CAPiTA study in 2015, showing the efficacy of the vaccine for the prevention of

vaccine-type community-acquired pneumonia (45.6%) and nonbacteremic (45%) pneumococcal pneumonia, and IPD (75%) caused by vaccine serotypes in subjects ≥ 65 years old, the EMA approved the indication for the prevention of pneumonia in adults aged ≥ 18 years.^{25,26}

Recent exploratory studies have shown a beneficial effect of PCV13 in reducing the number of exacerbations in COPD and other respiratory diseases.^{27,28} Results from a group of 90 COPD patients vaccinated with PCV13 and followed for 2 years in Spain showed a reduction of 50% in the number of severe exacerbations in the second year after immunization.²⁹ A prospective comparative open-label study carried out in Russia, evaluating PCV13 safety and effectiveness to prevent CAP in COPD patients compared with non-vaccinated patients, found in a group of 25 patients a 4.8-fold reduction in the incidence of exacerbations one year after vaccination.²⁸

The limitations of these preliminary results require larger studies, specifically designed for this purpose, to assess which subgroups might benefit most from this preventive approach.

The aim of this study is to generate evidence to support vaccination of COPD patients with PCV13 and/or against influenza in terms of clinical benefits and quality of life.

2.1 **STUDY DESIGN**

Prospective observational study, which will be carried out in 6 different geographical areas in Spain (Salamanca, Cantabria, Palma de Mallorca, Madrid, Barcelona and Seville), involving 1 hospital in each region.

Subjects identified with COPD will be invited to participate by investigators at the time of their routine follow-up visits. All therapies will be prescribed in line with routine clinical practice according to the updated National COPD Guidelines (GesEPOC),¹ indicating among other therapies active reduction of risk factors, and influenza and pneumococcal vaccination (with PCV13) in all patients with mild, moderate or severe COPD. All patients will be advised to quit smoking and recommended healthy lifestyle habits.

Study will include periodic visits for all patients, to complete a total follow up of 2 years.

2.2 **STUDY OBJECTIVES**

The study objectives are to:

- **Primary objectives**

1. Evaluate the impact of routine clinical practice vaccination with PCV13 on the reduction of the risk of moderate/severe COPD exacerbations, after 2 years of follow-up.
2. Determine which subgroup of patients (based on the severity of COPD) benefit most from vaccination with PCV13

COPD severity (GOLD)¹⁸

- GRADE 1: Mild/unknown [$FEV1 \geq 80\%$, $FEV1/FVC < 0.7$ or no spirometry record]
- GRADE 2: Moderate [$50\% \leq FEV1 < 80\%$, $FEV1/FVC < 0.7$]
- GRADE 3: Severe [$30\% \leq FEV1 < 50\%$, $FEV1/FVC < 0.7$]
- GRADE 4: Very severe [$FEV1 < 30\%$ or $FEV1 < 50\%$ plus respiratory failure, $FEV1/FVC < 0.7$])

- **Secondary objectives**

1. Evaluate the impact of influenza and PCV13 vaccination on the reduction of the risk of exacerbations
2. Evaluate the impact of vaccination with PCV13 on patients' quality of life
3. Evaluate the impact of vaccination with PCV13 on the decrease in FEV1
4. Estimate the potential savings for the healthcare system derived from vaccination of COPD patients with PCV13
5. Determine the prevalence of PCV13 vaccination in COPD patients.

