### **8.3.1 Study procedures**

#### **Visit 0: selection and recruitment**

- Obtain of signed informed consent document
- Confirmation of eligibility
- Assignment of subject number. Subject number will be assigned sequentially as the participants are included in the study. The number will be composed of 6 digits, first three will be the site code and last three the subject number.

Study authorized personnel will complete the case report form (CRF) for each of the subjects included. CRF (Annex 2) will be completed by an interview of the subject or review of clinical history and results of test/activities performed (as part of routine clinical practice)

Redacted

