4 HYPOTHESIS AND ROLE OF DISCUSSION

The statistical significance value is set at $p < 0.05$. The SPSS statistical package version 19.0 or later will be used.

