5 ANALYSIS SYSTEMS / POPULATIONS

Considering that 37% of COPD patients will have one moderate/severe exacerbation per year, and assuming that at least 35% of patients will follow their doctor's vaccination

recommendation,³ to have at least 200 vaccinated COPD patients with moderate/severe exacerbations, a total of 1541 eligible subjects should be included in the analysis.

With 35% of patients vaccinated with PCV13, enrolling 1541 eligible subjects with COPD would provide approximately 540 patients in the PCV13 cohort and 1000 patients in the unexposed cohort.

Assuming that 37% of unexposed patients will present one moderate/severe exacerbation per year,² with 70% of the patients remaining in the study after 1 year, this sample size would provide 91% power to detect a statistically significant reduction of 10% in moderate/severe COPD exacerbations with PCV13 after 1 year. Assuming an additional 30% dropout in the second year, the study sample size would provide 91% power to detect a statistically significant reduction of 14% in moderate/severe COPD exacerbations with PCV13 after 2 years.

Time	PCV13		Unexposed		Power	Retention rate
	Sample size	% exacerbation	Sample size	% exacerbation		
Enrollment	540		1000			
1 year	378	27%	700	37%	91.43%	70% from enrollment
2 years	264	60%	490	74%	91%	70% from year 1

5.1 **FULL ANALYSIS**

The statistical analysis of this study will be carried out with all those evaluable patients with COPD, recruited by the Spanish sites participating in the study and who meet the following selection criteria:

5.1.1 **Inclusion Criteria**

Patients must meet all of the following inclusion criteria to be eligible for inclusion in the study:

1. *Aged 18 years or older at the time consent is given*
2. *Patient diagnosed with COPD (any stage, subgroups for analysis will be based on COPD severity)*
3. *Evidence of a personally signed and dated informed consent document indicating that the patient has been informed of all pertinent aspects of the study.*
4. *Ability to understand and complete the required quality of life questionnaires*
5. *Patients with at least 2 years of previous clinical history available relating to (if applicable) history of moderate/severe exacerbations, influenza and pneumococcal vaccination history, comorbidities and previous treatments*
6. *Spirometry data* (maximum 6 months old, or if not available at enrollment, to be performed as per normal clinical practice at visit 1 ± one month)*

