The Student's t test, one-way ANOVA or its non-parametric equivalents, the Mann-Mann U test or Kruskal-Wallis H test will be used to determine if statistically significant differences are observed in NEPA, NEPA Mild, NEPA Moderate, NEPA Severe and NEPA Moderate/Severe according to the severity of COPD and type of patient (exposed/unexposed). In order to determine the impact of PCV13 vaccination on exacerbations, paired data comparisons will be made between (NEPA_pre_PCV13 vs. NEPA_post_PCV13) and (NEPA_pre_PCV13 (moderate/severe) vs. NEPA_post_PCV13 (moderate/severe)), using the Student's t-test for paired data or its non-parametric equivalent, the Wilcoxon test.

In order to study which subgroups of patients obtain a greater benefit from vaccination

with PCV13 according to COPD severity, paired data comparisons will be made between (NEPA_pre_PCV13 vs. NEPA_post_PCV13) and (NEPA_pre_PCV13 (moderate/severe) vs. NEPA_post_PCV13 (moderate/severe)), in each of the four patient subpopulations established based on disease severity.

In order to determine the factors associated with the presence of an exacerbator patient, a logistic regression model will be constructed, whose dependent variable is (exacerbator/non-exacerbator patient) and, as independent variables, all those possible factors that have been significant in the univariate models ($p_{value} < 0.25$), following the methodology of Hosmer-Lemeshow.

- ❖ Vaccine exposure (PCV13 yes/no)
- ❖ COPD severity (Grade I, Grade II, Grade III, Grade IV)
- ❖ Age
- ❖ Sex
- ❖ Time since diagnosis of the disease
- ❖ Patient with stable treatment for at least three months
- ❖

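### The exposed/unexposed comparisons do not account for hospital, so they may be confounded if PCV13 uptake and recorded exacerbation risk vary together across the six sites

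*SAP*

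**What the plan says.** SAP section 2.1 and Protocol section 8.1 describe a cohort from six regions, "involving 1 hospital in each region", so hospital and region are the same factor. SAP section 8.1 evaluates results as a cohort study with unvaccinated patients as the unexposed group, and SAP section 5 sizes the study for that contrast.

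The planned exposed/unexposed effectiveness analyses are:

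- **Two-sample tests** (t-test or Mann-Whitney, no covariates) of NEPA (SAP 8.2.3.1), percentage change in FEV1 (8.2.3.2), costs (8.2.3.6), and SGRQ and CAT (8.2.3.7).
- **Logistic regression of any exacerbation** (SAP 8.1). PCV13 is entered with variables significant univariately. The examples are demographics, influenza vaccination and smoking, and the list is left open. Phenotype, comorbidities, severity and FEV1 are named as potential confounders.
- **Logistic regression of exacerbator status** (SAP 8.2.3.1). Candidates are screened at p < 0.25. The list gives vaccine exposure, severity, age, sex, "Time since diagnosis of the disease" and stable treatment, then a blank bullet.

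Hospital appears in none of these. It is also absent from the analysis groups in SAP 8.2.1 and from the limitations in Protocol 8.9. It is nevertheless recorded: in the six-digit subject number, "first three will be the site code and last three the subject number" (Protocol 8.3.1).

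Separately, SAP 8.2.3.1 assigns the impact of vaccination on exacerbations to a paired pre/post NEPA comparison within vaccinated patients, repeated by severity grade. SAP 8.2.3.6 does the same for costs.

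**The concern.** The documents make both links of a confounding path plausible.

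- **Hospital and exposure.** Vaccination is left to clinical practice, and Protocol 8.1 counts among the controls patients whose physicians did not recommend PCV13. Exposure therefore depends partly on the physician, and physicians belong to hospitals.
- **Hospital and outcome.** Exacerbations are those recorded at hospital or in primary care (Protocol 8.3). Access to the primary-care database linked to each hospital is described as possible and common, not universal (Protocol 8.2). A moderate exacerbation by definition involves no admission (Protocol, definitions under Table 1), so its capture may depend on that local access. Case mix may also differ by hospital.

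If hospitals with high uptake also record fewer exacerbations, a pooled comparison shows a benefit where there is none. If uptake and recorded risk rise together, it hides a real one.

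**Working it through.** **The plan's own figure.** Inputs from SAP sections 4 and 5: "approximately 540 patients in the PCV13 cohort and 1000 patients in the unexposed cohort"; 70% retained at year 1, giving 378 and 700; "Assuming that 37% of unexposed patients will present one moderate/severe exacerbation per year"; and a 10-point reduction to 27%. "The statistical significance value is set at" p < 0.05; sidedness is not stated, and two-sided is assumed.

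- Pooled risk = (378 × 0.27 + 700 × 0.37)/1078 = 0.335.
- SE under no difference = √[0.335 × 0.665 × (1/378 + 1/700)] = 0.0301.
- SE under the planned difference = √[0.27 × 0.73/378 + 0.37 × 0.63/700] = 0.0292.
- Power = Φ[(0.10 − 1.96 × 0.0301)/0.0292] = Φ(1.40) = 91.9%, against 91.43% stated.

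The figure reproduces as an unadjusted two-proportion calculation with no allowance for hospital.

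**Bias from pooling.** Take six equal hospitals with uptake u and annual risk r, and no vaccine effect within any hospital:

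- crude risk, exposed = Σur/Σu
- crude risk, unexposed = Σ(1 − u)r/Σ(1 − u)
- spurious benefit = −Cov(u, r)/[ū(1 − ū)]

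The last line shows the condition: the bias is zero unless uptake and risk both vary across hospitals and are correlated.

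**Assumed inputs.** The documents give only overall figures (35% uptake, 37% risk), so the spreads below are assumptions around those means.

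- Uptake in both sets: 0.15, 0.25, 0.30, 0.35, 0.45, 0.60 (sum 2.10; complement 3.90).
- Wider risk set: 0.45, 0.42, 0.38, 0.36, 0.32, 0.29.
- Milder risk set: 0.40, 0.39, 0.37, 0.37, 0.35, 0.34.

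| Risk set | Exposed | Unexposed | Difference | RR |
|---|---|---|---|---|
| Wider | 0.7305/2.10 = 34.8% | 1.4895/3.90 = 38.2% | 3.4 points | 0.91 |
| Milder | 0.7595/2.10 = 36.2% | 1.4605/3.90 = 37.4% | 1.3 points | 0.97 |

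Check by the covariance form: 0.00775/(0.35 × 0.65) = 0.034 and 0.00292/(0.35 × 0.65) = 0.013.

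**Chance of a false finding.** With 378 and 700 patients and 37% risk, SE = √[0.37 × 0.63 × (1/378 + 1/700)] = 3.1 points. A bias of 3.4 points gives p < 0.05 in about 20% of studies, and 1.3 points in about 7%, instead of 5%.

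**Sensitivity to the spread.** Uptake and risk are evenly spaced around their means over six equal hospitals, inversely related, with no true effect and 1078 patients:

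| Uptake / risk half-range (points) | Spurious benefit, pooled | p < 0.05, pooled | Stratified by hospital |
|---|---|---|---|
| only one of the two varies | 0 | 5% | 0, 5% |
| ±10 / ±5 | 1.0 points | 6% | 0, 5% |
| ±20 / ±10 | 4.1 points | 26% | 0, 5% |
| ±30 / ±15 | 9.2 points | 85% | 0, 5% |

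If uptake and risk instead rise together at ±20 / ±10, a true 10-point effect appears as 5.9 points and power falls to 50%.

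**Cost of stratifying.** Power for a true 10-point effect, stratified by hospital, is 92.8% with no spread. It is 90.6–91.5% at ±20 / ±10 and 86.3–89.5% at uptake ±30 over the risk spreads tried. The loss is 1.3–2.2 points at moderate spread and at most 6.5 at the widest.

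These figures concern exacerbation risk at one year. None were computed for FEV1, costs or quality of life.

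**The case against.** The strongest reply is that the SAP's named impact analysis is not exposed to this problem. The paired pre/post comparisons of NEPA and costs use vaccinated patients as their own controls, and Protocol 8.7 also frames impact as before versus after. Stable hospital differences in uptake or recording largely cancel there. This stands in full; those analyses may have other weaknesses, but not this one. It does not cover the exposed/unexposed contrast, for which the study is sized and which SAP 8.1 presents as the way results are evaluated.

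Second, the plan contains standardising features: one national guideline, one exacerbation definition, scheduled enquiry at all six visits from month 0 to 24, and an electronic CRF monitored against source documents. These make very wide spreads less likely, but do not exclude site differences. FEV1 is compared as change from baseline, so a fixed hospital offset matters less there than for NEPA or costs.

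Third, the covariate lists are open, so hospital is unspecified rather than excluded. That is true of the logistic models, but an open list does not prespecify hospital, and entry would depend on univariate screening. It does nothing for the two-sample tests, which take no covariates.

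Fourth, the bias is conditional. This also stands: no hospital-level uptake or exacerbation figure is given, and both main scenarios assume uptake and risk in strictly opposite order.

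**Conclusion.** The exposed/unexposed comparisons of NEPA, FEV1, costs and quality of life, and both logistic models, do not account for hospital. They may be confounded if uptake and recorded risk both differ by hospital and are correlated. Direction and size are unknown. Under the assumed inverse spreads with no true effect, the spurious benefit is about 1.3 to 3.4 points, or 13% to 34% of the planned 10-point effect. This is an inexpensive improvement to the plan, not a defect that invalidates it.

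Two stronger readings are tempting and not supported. A reader might infer that every estimate of the vaccine effect is confounded by region; the paired analyses in vaccinated patients largely escape, and for the rest the documents do not show that the conditions are met. A reader might also take the 9-point bias and 85% false-positive rate in the last table row as what to expect. That row needs uptake from about 5% to 65% and risk from 22% to 52%, perfectly inversely ordered, and nothing in the documents supports such a spread.

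**What to change.** Amend the SAP as follows:

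- Take hospital from the site code in the subject number and force it as a fixed effect into both logistic models, exempt from univariate screening.
- Replace or supplement the exposed/unexposed two-sample tests of NEPA, FEV1, costs and quality of life with hospital-stratified or hospital-adjusted versions. These are tests, not models, so adding a term is not enough. Options are a rank test stratified by hospital or a regression on exposure and hospital.
- Tabulate PCV13 uptake and exacerbation rates by hospital, so that readers can see whether the conditions for bias are present and whether any hospital has too few vaccinated or unvaccinated patients to inform the comparison.

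The paired analyses need no change on this account. No new data are required. The cost is five parameters against 1078 patients expected at year 1, some extra programming and tables, and a small power loss: about 1–2 points at moderate uptake spread and up to about 7 at the widest spread tried.
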